#### 4.2.1 Treatment Naming, Grouping and Ordering

The six treatment arms defined in the protocol will be labelled and ordered (unless specified otherwise) in the outputs by means of age cohorts and dose administered as provided in table below.

**Table 1 Treatment Group Labelling and Order**

Order	Treatment Group [1]	Cohort	Dose	Treatment Group Label [2]
1	Arm-1	Adults	5*E10 vp	Adults, 5*E10 vp (Arm-1)
2	Arm-2		1*E11 vp	Adults, 1*E11 vp (Arm-2)
3	Arm-3		2*E11 vp	Adults, 2*E11 vp (Arm-3)
4	Arm-4	Elderlies	5*E10 vp	Elderlies, 5*E10 vp (Arm-4)
5	Arm-5		1*E11 vp	Elderlies, 1*E11 vp (Arm-5)
6	Arm-6		2*E11 vp	Elderlies, 2*E11 vp (Arm-6)

[1] As indicated in protocol. [2] As displayed in outputs.

Summaries will be grouped depending on data (e.g. demographics, AE, safety lab, etc.) as well as the type of delivery, i.e. interim analysis 1 and 2 and post database lock. Grouping method is indicated for each data type and each delivery in the following.

**Table 2 Grouping: Subject Classification, Disposition, Demographics, Exposure, AEs and Categorical Safety**

Delivery									
IA 1	Arm-1	Arm-2	Arm-3	Total					
IA 2	Arm-4	Arm-5	Arm-6	Total					
FA	Arm-1	Arm-2	Arm-3	Arm-4	Arm-5	Arm-6	Total		
FA [1]	Arm-1	Arm-2	Arm-3	Adult Total	Arm-4	Arm-5	Arm-6	Elderly Total	Total

IA: Interim analysis. FA: Final analysis.

[1] AE and Categorical Safety only

**Table 3 Grouping: Safety (excluding AEs and Categorical Safety), Immunogenicity, Labs and Diary Data**

Delivery						
IA 1	Arm-1	Arm-2	Arm-3			
IA 2	Arm-4	Arm-5	Arm-6			
FA	Arm-1	Arm-2	Arm-3	Arm-4	Arm-5	Arm-6

IA: Interim analysis. FA: Final analysis.

For interest of space table displays treatment arms instead of treatment labels, but outputs will display treatment labels.

#### 4.2.2 Imputation of Missing and Incomplete Dates/Times

Every effort will be made to collect complete dates for all study assessments. The following date imputation rules will be applied for missing or partial dates:

- If month and year available, set start date to latest of (1st of the month, first dose date), if end date is complete and imputed start date > end date, set imputed start date to end date – 1
- If year available: Set start date to latest of (January 1st, first dose date), if end date is complete and imputed start date > end date, set imputed start date to end date – 1
- If start date is completely missing, set to first dose date, if end date is complete and imputed start date > end date, set imputed start date to end date – 1.

Completely missing time information will be imputed as 00:00. Partially missing time information with missing hour (xx:mm) or minute (hh:mm) part will be imputed as 00:mm or hh:00, respectively. Missing part will be shown as NK in the listings (where NK = Not Known).

If time is not collected and date of assessment is the same as the first dose date, then assessment will be assumed to be collected prior to treatment unless schedule of assessments and protocol indicate planned collection is always after dosing.

Any AEs with incomplete start and end dates/times will be treated as follows:

Adverse events with unknown start and/or end times (but where the date is known) will be imputed with a time of 00:00 h for the tabulations but will be shown as NK:NK in the listings (where NK = Not Known).

Adverse events with completely unknown start dates will be considered as treatment-emergent for the tabulations and will be shown as NK in the listings. Partially complete AE dates will not be imputed in the listings and the available day, month and year components will be used to determine if an adverse event is treatment-emergent taking the first dosing date and end of study date as references.

Imputing partial AE and prior/concomitant medication start dates:

- a) If the year is unknown, the date will not be imputed and will be assigned a missing value.
- b) If the month is unknown, then:
  1. If the year matches the first dose date, then impute to the month and day of the first dose date.
  2. Otherwise, assign 'January'.
- c) If the day is unknown, then:
  1. If the month and year match the first dose date, then impute to the day of the first dose date.
  2. Otherwise, assign '01'.

Imputing partial AE and prior/concomitant medication stop dates:

- a) If the year is unknown, the date will not be imputed and will be assigned a missing value.
- b) If the month is unknown, then assign 'December'.
- c) If the day is unknown, then impute to the last day of the month.

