#### **4.8 Prior and Concomitant Medications**

Concomitant medications will be analyzed using the SAF. Concomitant medications will be coded using the World Health Organization-Drug Dictionary (WHO-DD B3) Version March 2020 and will be classified by Anatomical Therapeutic Chemical (ATC) categories.

Medication start and stop dates will be compared to the date of first dose of study medication to allow medications to be classified as either Prior only, both Prior and Concomitant, or Concomitant only. Medications starting after the completion/withdrawal date will be listed but will not be classified or summarized. Medications that start and stop prior to the date of first dose of study medication will

be classified as Prior only. If a medication starts before the date of first dose of study medication and stops on or after the date of first dose of study medication, then the medication will be classified as both Prior and Concomitant. Medications will be classified as Concomitant only if they have a start date on or after the date of first dose of study medication.

If medication start and/or stop dates are missing or partial, the dates will be compared as far as possible with the date of first dose of study medication. Medications will be assumed to be Concomitant only, unless there is clear evidence (through comparison of partial dates) to suggest that the medication started prior to the first dose of study medication. If there is clear evidence to suggest that the medication started prior to the first dose of study medication, the medication will be assumed to be both Prior and Concomitant, unless there is clear evidence to suggest that the medication stopped prior to the first dose of study medication. If there is clear evidence to suggest that the medication stopped prior to the first dose of study medication, the medication will be assumed to be Prior only.

Prior and concomitant medications as recorded in the Concomitant Medication eCRF will be presented in by-patient data listing. Listing will include ATC Level 1/Treatment Name/Name, dose, frequency and route, start/stop date and classification (prior, previous or both).

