#### 4.11.1 Adverse Events

Adverse events (AEs) will be coded using the Medical Dictionary for Regulatory Activities (MedDRA) Version 23.0.

An AE is any untoward medical occurrence in a study subject administered an IMP which does not necessarily have a causal relationship with this treatment. An AE can therefore be any unfavorable and unintended sign (including a clinically significant abnormal laboratory finding), symptom, or disease temporally associated with the use of an IMP, whether or not considered related to the IMP. Adverse events may include the onset of new illness and the exacerbation of pre-existing conditions.

Other untoward events occurring in the framework of a clinical study will be recorded as AEs, e.g. those occurring during treatment-free periods (including Screening or post-treatment Follow-up periods), in association with study-related procedures and assessments or under placebo.

Concomitant illnesses, which existed before entry into the clinical study, will not be considered AEs unless they worsen during the treatment period. Pre-existing conditions will be recorded as part of the subject's medical history.

A treatment-emergent adverse event (TEAE) is defined as an AE that begins or worsens in severity in 28 days after study drug administration.

Adverse event with 'No Relationship' or 'Unlikely Related' causality will be evaluated as not related (relationship = No), otherwise (including missing causality) AE will be evaluated as related (relationship = Yes).

Adverse events with completely unknown start dates will be considered as treatment-emergent for the tabulations and will be shown as NK in the listings. Partially complete AE dates will not be imputed in the listings and the available day, month and year components will be used to determine if an adverse event is treatment-emergent taking the first dosing date and end of study date as references.

Solicited adverse reactions are foreseeable AEs following vaccination with GRAd-COV2 including the following AEs: injection site pain, erythema, warmth, swelling, pruritus, myalgia, arthralgia, headache, fatigue, fever, feverishness, malaise and nausea. Solicited adverse reaction is recorded as such on the corresponding AE's eCRF.

Adverse events of special interest (AESI) are any grade  $\geq 3$  abnormalities on safety blood test according to Common Terminology Criteria for Adverse Events v.5.0 (CTCAE, see section [4.11.3](#)).

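### Adverse events with incomplete start dates are judged treatment-emergent up to end of study instead of day 28, and the AE start-date rule has no end-date check and no stated precedence over a conflicting general rule

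*SAP*

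**What the plan says.** SAP 4.11.1 sets the window: "A treatment-emergent adverse event (TEAE) is defined as an AE that begins or worsens in severity in 28 days after study drug administration". Further down that section, and also in 4.2.2, an AE with an incomplete date is classified from whatever parts of the date are known, as "treatment-emergent taking the first dosing date and end of study date as references". SAP 4.2 takes end of study to be the final assessment on record after dosing, which the schedule places at week 24.

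SAP 4.2.2 contains two sets of start-date rules.

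- **General bullets**, introduced by "The following date imputation rules will be applied for missing or partial dates". With only the day missing: "If month and year available, set start date to latest of (1st of the month, first dose date". With nothing known: "If start date is completely missing, set to first dose date". Each bullet has a safeguard: "if end date is complete and imputed start date > end date, set imputed start date to end date", less one day.
- **AE and medication list.** With only the day missing: "If the month and year match the first dose date, then impute to the day of the first dose date"; any other month takes its first day. With the month also missing, the dose date is used if the year matches, otherwise January. With the year unknown, the date stays missing. There is no check against the end date.

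Both 4.2.2 and 4.11.1 also count every AE with a wholly unknown start as treatment-emergent. No sentence says which set of rules prevails.

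**The concern.** The TEAE status of an incompletely dated event depends on which sentence the programmer follows and on whether the day was recorded. Two kinds of event can be tabulated as TEAEs although the record itself shows that they are not: those known to have started after day 28, and those known to have ended before vaccination.

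Such records can exist. SAP Table 5 schedules AE reporting from screening to week 24, and SAP 4.11.1 says that events in the screening and follow-up periods are recorded.

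Safety is the primary objective. Protocol 4.2.1 endpoint C is unsolicited AEs over 28 days. The SAP has no separate unsolicited-AE table, so the 28-day TEAE tables are, by inference, its only output matching that endpoint.

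**Working it through.** The plan states no figure here that could be reproduced, so the rules were applied as written.

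**Inputs.** TEAE window: 28 days (SAP 4.11.1), taken as onset minus dose of 0 to 28. Follow-up: 24 weeks = 24 × 7 = 168 days (Protocol synopsis), with a ±14-day window at week 24 (SAP Table 5). Arm size: 15 (Protocol section 5). Assumed for illustration: dose on 15 Sep 2020, so day 28 is 13 Oct 2020 and week 24 is 2 Mar 2021. The share of AEs with incomplete dates is not given.

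**Step 1: window length.** 168 / 28 = 6 times the defined window. With the visit window the range is (168 − 14) / 28 = 5.5 to (168 + 14) / 28 = 6.5.

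**Step 2: single records.** Each cell gives the imputed start and whether the event is a TEAE. The two imputation columns use the 28-day window. The last column is the stated rule for incomplete or unknown AE starts, applied to the start date only.

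| Recorded | General bullets | AE/medication list | First dose to end of study |
|---|---|---|---|
| Nov 2020 | 1 Nov, no | 1 Nov, no | yes |
| Sep 2020, ended 10 Sep | 9 Sep, no | 15 Sep, yes | yes |
| Start unknown, ended 10 Sep | 9 Sep, no | left missing | yes (always) |
| Aug 2020, ongoing | 15 Sep, yes | 1 Aug, no | no |
| Sep 2020, ongoing | 15 Sep, yes | 15 Sep, yes | yes |
| Oct 2020 | 1 Oct, yes | 1 Oct, yes | yes |

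- Row 1: 1 November is day 15 + 31 + 1 = 47, so no November date can fall within 28 days. A complete November date is not a TEAE; one with the day missing is.
- Row 2: the AE list starts the event 15 − 10 = 5 days after it ended.
- Row 3: the event ended before vaccination and is still a TEAE.
- Row 4: the two sets of rules give opposite answers.

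**Step 3: enumeration.** Every dose date in the 365 days from 1 Jul 2020 was crossed with every onset day shown, with the day of the month missing. Events are ongoing unless stated. Entries are the share called TEAE.

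| True onset (days from dose) | Combinations | General bullets | AE/medication list | First dose to end of study |
|---|---|---|---|---|
| −28 to −1 | 365 × 28 = 10,220 | 100% | 52.3% | 52.3% |
| −28 to −4, resolved 3 days later, before dosing | 365 × 25 = 9,125 | 0% | 47.4% | 47.4% |
| 0 to 28 | 365 × 29 = 10,585 | 100% | 100% | 100% |
| 29 to 168 | 365 × 140 = 51,100 | 10.5% | 10.5% | 100% |

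With a 28-day upper reference the last row falls from 100% to 10.5%. What remains is onsets in a month that began inside the window, which cannot be told apart without the day. With an end-date check the second row falls from 47.4% to 0%. True onsets on days 0 to 28 are unaffected.

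These shares are conditional on a missing day and weight every onset day equally. They are not rates expected in the trial.

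**Step 4: weight of one subject.** 1 / 15 = 6.7%.

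**The case against.** **Specific over general.** The list headed for AEs and medications can fairly be read as overriding the general bullets. That reading is natural. It removes the August conflict and any medication problem, since SAP 4.8 has its own rule for partial medication dates: a drug that clearly started before dosing is handled as "the medication will be assumed to be both Prior and Concomitant, unless there is clear evidence" that it also stopped before dosing. It does not remove the end-of-study reference, which is itself written for AEs and appears twice. It also leaves the start-after-end case, which arises within the AE list.

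**The 28-day definition comes first.** One could treat the end-of-study sentence as loose wording and apply the definition, in which case November is not a TEAE. That is probably what was meant. But the sentence is the only one that says how known date parts decide status, and it names a different upper limit.

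**Few records.** Daily diaries for four weeks, visits at day 2 and weeks 1, 2 and 4, and eCRF queries should keep incomplete dates rare inside the 28 days. This stands and limits the practical effect.

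Three stronger readings are tempting and are not supported:

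- A reader might infer that every pre-vaccination event with a missing day becomes a TEAE under the general bullets. The 100% holds only for events that are ongoing at dosing or lack a complete end date. With the cap in force, events that resolved before dosing give 0%.
- A reader might infer that related-TEAE counts are inflated. Relatedness comes from the investigator's causality rating, which date imputation does not change. A misclassified event enters those counts only if it was rated possible or higher, or if causality is missing.
- A reader might object to counting dose-month events at all. With no end date before dosing, that is a usual conservative convention.

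**Conclusion.** The point holds as two drafting defects that misclassify events. First, the end-of-study reference contradicts the 28-day definition and makes TEAEs of events that cannot lie in the window. Second, 4.2.2 gives two start-date rules without precedence, and neither the AE list nor the unknown-start rule checks a complete end date, so events that resolved before vaccination can be counted.

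The errors that remain once the AE list is taken to govern add events to the TEAE tables. They are confined to AEs with partial or missing dates, and the number affected cannot be computed from the documents. It may be very few, but a single subject moves an arm's rate by 6.7 percentage points. The trial is descriptive, so no test or error rate is involved. The link to endpoint C is an inference, because the TEAE tables pool solicited and unsolicited events. The text should be corrected because the rule is wrong as written and the repair is cheap; a material distortion of the safety results is not shown.

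**What to change.** 1. In SAP 4.2.2 and 4.11.1, replace the end of study date with first dose date + 28 days as the upper reference. A month-only or year-only start is then treatment-emergent only if its known parts are compatible with that window.
2. State in 4.2.2 that the AE/medication list governs AEs and medications, and that the opening bullets do not apply to them.
3. Add to that list, and to the rule for wholly unknown AE starts: if a complete end date precedes the first dose, the event is not treatment-emergent; and any imputed start later than a complete end date is set to that end date.

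Dose-month events with no end date before dosing stay TEAEs. Known parts and imputed dates then agree: a later month or year overlaps the window exactly when its first day is on or before day 28, and an earlier one never does.

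The cost is a few sentences in the SAP, a few lines of derivation code, and a rerun of any TEAE tables already produced. No new data are needed.

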#### 4.3 Software

All report outputs will be produced using SAS® version [9.4] or a later version in a secure and validated environment.

All report outputs will be provided to the Sponsor in RTF and PDF format.

## 4.4 Study Subjects

### 4.4.1 Disposition of Subjects

A clear accounting of the disposition of all subjects who enter the study will be provided, from screening to study completion.

An overview will be provided by treatment and overall on the number and percentage of subjects with ICF. The summary will include the number and percentage of subjects who entered, completed or discontinued (with reason for discontinuation) the study. Summary will be provided for each site and overall.

Summaries will include the number and percentage of subjects entering, completing and withdrawing from the study. Withdrawals from the study will also be summarized by major reason.

By-subject listings of eligibility and randomization details, visit dates, and withdrawal details (including reason for discontinuation and on study duration prior to discontinuation) will also be provided.

### 4.4.2 Protocol Violations

Protocol deviations are defined in a study specific Protocol Deviation Specification document.

Protocol deviations will be discussed during Data Review Meeting(s) (DRM) between PAREXEL and Sponsor, per the applicable SOPs (SOP-EPD-WW-012 and SOP-GDO-WW-017). All recorded PDs will be classified to minor/major/none and determined whether such deviations may warrant exclusion of a subject from the statistical analyses. Decisions made regarding the exclusion of subjects and/or subject data from analyses will be documented in the DRM report and approved by the Sponsor prior to database lock (DBL).

A summary of the number and percentage of subjects with major protocol deviation will be provided by treatment and protocol deviation for each site and overall.

By subject listing of protocol deviations will be provided for all screened subjects. This listing will be presented by treatment group and include subject identifier, visit (of occurrence), verbatim protocol deviation, protocol deviation code and classification (major/minor).

#### 4.5 Analysis Sets

The safety summaries and analyses will be based on the Safety Analysis Set (SAF). The Safety Set is defined as all subject received any amount of study drug. Analyses using SAF will be performed by ‘as treated’ approach i.e. by actual treatment received.

The immunogenicity summaries and analyses will be based on the Immunogenicity Analysis Set (IAS). The immunogenicity analysis set is defined as all subject received any amount of study drug and have at least one non-missing post baseline immunogenicity evaluation. Subjects with any major protocol deviation thought to interfere with either the mechanism of action or immunogenicity test measurements will be excluded from IAS. Analyses using IAS will be performed by ‘as treated’ approach i.e. by actual treatment received.

A summary of the number and percentage of subjects assigned to each analysis set by treatment and overall will be provided for all subjects enrolled.

A by-subject listing of analysis set details will be provided for all subject enrolled. This listing will be presented by parts and dose group and include subject identifier, inclusion/exclusion flag for each analysis set and reason for exclusion, if applicable. This listing will be provided for all subjects dosed.

DRM will be held after the last data has been entered into the clinical database (DB) and prior to DB hard lock (DBHL). The primary purposes of the DRM are to:

- Confirm that the database is ready to be hard locked.
- Agree assignment of each enrolled subject to the analysis sets defined by the criteria described in Statistical Analysis Plan (SAP, Section 4.5), also known as analysis sets classification.

Results and decisions made during the meeting will be summarized in the DRM report which will be signed off by PAREXEL representatives and the Sponsor.

#### 4.6 Demographics and Baseline Characteristics

Age will be calculated as the number of complete years between a subject's birth date and the date of informed consent.

Descriptive statistics (see Section 4.2Error! Reference source not found.) for demographics and other baseline characteristics will be presented for subjects assigned to SAF. All descriptive

summaries will be presented by treatment and overall. Unless otherwise specified, percentages (%) will be based on the number of patients assigned to SAF with data available.

Demographics will be summarized, including:

- Age (years)
- Sex
- Race (American Indian or Alaska Native, Asian, Black or African American, Native Hawaiian or Other Pacific Islander, White, Other/Specification )
- Ethnicity (Hispanic or Latino, Not Hispanic or Latino, Not Stated, Unknown)
- Other Baseline characteristics, as recorded in the Vital Signs - Height and Weight eCRF at Screening
  - Height (cm).
  - Weight (kg).
  - Body mass index (BMI) (kg/m^2).

#### **4.7 Medical History and Concomitant Illnesses**

Medical history/current medical conditions will be presented for all subjects in SAF according to the Medical Dictionary for Regulatory Activities (MedDRA version 23.0 or higher) primary system organ class (SOC) and preferred term (PT), regardless of whether the status is reported as ongoing or not ongoing at visit Day 0. Medical history/current medical condition, start date of event and ongoing status (yes/no) of each medical history/current medical condition as pre-specified in the Medical history eCRF will be presented in by-subject data listing.

